5.9 Data Submission for Cancer Prevention Companion Studies (CALGB 71002)

At registration, patients may elect to enroll on the cancer prevention studies ([Appendices IV and V](#)) by consenting to question #1. These studies will require patients to complete a Diet and Lifestyle survey and agree to the submission of their colonoscopy and pathology reports as described below.

Diet and Lifestyle Survey:

Surveys will be sent by [REDACTED] (see below) to individual treatment centers within 2 weeks of registration. Versions of the surveys are available in Spanish and French – please email [REDACTED] requesting these versions if required for the patient. Patients should complete the first survey within 6 weeks of randomization. Patients should also complete questionnaires 14-16 months from randomization. It is recommended that the surveys be completed during a physician visit, likely during the infusion of chemotherapy. Questions regarding the survey should be directed to [REDACTED]. Completed surveys should be mailed by the institutional CRA to the following address:

[REDACTED]
 [REDACTED]
 [REDACTED]
 [REDACTED]
 [REDACTED]
 [REDACTED]

Colonoscopy and Pathology Reports:

According to NCCN and US Multi-Society Task Force guidelines, it is recommended that patients have a colonoscopy performed within 12 months of diagnosis. Clinical considerations should dictate the exact timing (i.e., if the patient’s initial colonoscopy at diagnosis was not a complete exam or the patient did not have a colonoscopy at diagnosis, guidelines suggest the first post-treatment colonoscopy be performed sooner than 12 months after surgery – typically after completion of adjuvant FOLFOX). A second post-treatment colonoscopy should be performed within 3 years of the first post-treatment colonoscopy, but may be performed earlier based on findings from the first colonoscopy as well as other clinical conditions. Earlier timing should be dictated by the clinical judgment of the gastroenterologist, oncologist and/or surgeon.

All colonoscopy reports obtained within the first 6 years after randomization should be submitted via Medidata Rave®. If any biopsies were taken during those colonoscopies, those pathology reports should also be submitted via Medidata Rave®. See [Section 5.7](#) for data submission instructions.

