7.0 TREATMENT PLAN

Initiation of treatment must begin within 14 days after randomization. While not strictly an eligibility criterion, it is strongly recommended that patients begin treatment between 21 - 56 days after surgery. For patients who fall outside of this range or for any treatment-related questions, contact the Alliance or SWOG Study Chair.

This is a randomized, double-blind trial. No blinded starter supplies will be available for this study. Initial blinded, patient-specific clinical supplies of celecoxib / placebo will be shipped from the Pharmaceutical Management Branch (PMB) to the registering investigator at the time of patient randomization and should arrive within 7 to 10 days of randomization (see [Section 9.4](#)).

One cycle will be defined as 14 days of treatment. Cytotoxic chemotherapy will consist of 6 or 12 cycles of FOLFOX and daily celecoxib/placebo. Celecoxib/placebo will start by Day 1 of cycle 2 of FOLFOX.

7.1 FOLFOX, every 2 weeks.

- **Oxaliplatin** 85 mg/m² IV over two hours, **followed by**
- **Leucovorin** 400 mg/m² IV over two hours. Alternatively, leucovorin may be administered (via separate infusion containers) concurrently with oxaliplatin, **followed by**
- **5-FU** 400 mg/m² IV bolus, then 2400 mg/m² continuous IV infusion over 46-48 hours.

Patients receiving oxaliplatin on this study should be counseled to avoid cold drinks, chewing of ice chips, and exposure to cold water or air because the neurotoxicity often seen with oxaliplatin appears to be exacerbated by exposure to cold. The period of time during which the patient is at risk for these cold-induced sensory neuropathies is not well documented. Patients should exercise caution regarding cold exposure during the treatment period. Peripheral sensory neuropathies can occur at any time after receiving oxaliplatin therapy.

Continuous infusion 5-FU should be administered as specified, though early pump shut-offs do not need to be reported on forms unless >10% of dose was not administered.

In the event of a leucovorin shortage, refer to the CALGB 80702 study page, which can be found on the Alliance and CTSU websites.

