1.0 OBJECTIVES

1.1 Assess the influence of diet, body mass index, physical activity and other lifestyle habits on disease-free and overall survival among patients with stage III colon cancer.

1.2 Assess the influence of baseline plasma C-peptide, insulin-like growth factor binding protein-1 (IGFBP-1), insulin-like growth factor-1 (IGF-1), IGFBP-3, and adiponectin on disease-free survival in patients with stage III colon cancer.

1.3 Assess whether tumoral expression of phospho-Akt (pAkt) and fatty acid synthase (FASN) and KRAS and PI3K mutational status modifies the relation between measures of energy balance (e.g., dietary insulin index, obesity, physical activity, plasma C-peptide) and patient survival.

1.4 In exploratory analyses, assess the influence of diet, obesity, physical activity, and other lifestyle habits on the risk of toxicity associated with chemotherapy.

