It is hypothesized that specific tumoral alterations modify the effect of measures of energy balance (e.g., dietary insulin index, obesity, physical activity, plasma C-peptide) on patient survival. For the analysis of tumoral alterations (**Objective 1.3**), all patients who had a tumor block available for analysis and data on the relevant exposure or plasma analyte will be included. All tumors will be categorized as having FASN and pAkt overexpression versus no overexpression, and KRAS and PIK3CA mutated versus wild type. Within each of binary category of FASN expression and pAkt expression, and KRAS and PIK3CA mutational status, we will examine the influence of an exposure or plasma analyte divided into tertiles on DFS and OS. Tertiles will be utilized instead of quintiles of to maximize the ability to detect an association within each subgroup. Cox proportional hazards models will be used to calculate HRs and 95% CIs for DFS and OS, adjusted for other prognostic factors. Tests for statistical interaction will be performed by entering into the model the cross-product term of the relevant exposure or plasma analyte as a continuous variable with the molecular alteration as a binary variable (overexpressed versus not; mutated versus wild type).

In exploratory analyses (**Objective 1.4**), the influence of diet and other factors on toxicities associated with adjuvant therapy will be assessed. Data from the questionnaire obtained during adjuvant therapy will be used for these analyses. Using logistic regression models, odds ratios and 95% CIs for the specific toxicity will be the measure of association with an exposure, adjusted for multiple potential confounders simultaneously.

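### The exploratory lifestyle-toxicity analysis does not require toxicity to follow the questionnaire, so reverse causation is possible, mainly for physical activity and supplement use

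*Combined protocol and SAP*

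**What the plan says.** Appendix IV, Objective 1.4, reads: "In exploratory analyses, assess the influence of diet, obesity, physical activity, and other lifestyle habits on the risk of toxicity associated with chemotherapy". Section 4.4 of that appendix gives the method: "Using logistic regression models, odds ratios and 95% CIs for the specific toxicity will be the measure of association with an exposure", adjusted for potential confounders. It names the exposure source: "Data from the questionnaire obtained during adjuvant therapy will be used for these analyses".

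The timing comes from the main protocol. Section 5.9 says: "Patients should complete the first survey within 6 weeks of randomization". It adds: "It is recommended that the surveys be completed during a physician visit, likely during the infusion of chemotherapy". Section 7.0 says: "Initiation of treatment must begin within 14 days after randomization", and "One cycle will be defined as 14 days of treatment". A second form comes much later: "Patients should also complete questionnaires 14-16 months from randomization".

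Appendix V, Objective 1.3, relates physical activity and vitamin supplements to the incidence and resolution of neuropathy. It draws on the same questionnaire (its Section 3.3) and on logistic models (its Section 4.0).

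The plan does guard against reverse causation elsewhere. For the main effects of plasma markers, Appendix IV, Section 4.4, and Appendix II, Section 5.0, drop patients who recurred or died within three months of the blood sample and vary the lag. Those rules concern plasma levels against recurrence or death. None is stated for Objective 1.4.

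**The concern.** A logistic model of whether a toxicity ever occurred carries no time order. A patient who became inactive, or began taking supplements, because of toxicity in the first cycles is analysed in the same way as one whose habits came first. Adjusting for confounders does not repair a reversed sequence. What is at stake is the reading of the activity and supplement odds ratios: one produced by symptoms could be reported as a lifestyle effect on toxicity risk.

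**Working it through.** The plan states no sample size, power or alpha for Objective 1.4, so there is no figure to reproduce. The check has three parts.

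**1. Treatments given before the questionnaire.** Count randomization as day 0. FOLFOX starts between day 0 and day 14 and repeats every 14 days; the form is due by day 42.

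- Start on day 0, form on day 42: treatments on days 0, 14 and 28 come first, so 3 (a fourth is due that day).
- Start on day 14, form on day 42: treatments on days 14 and 28 come first, so 2 (a third is due that day).
- Form completed at or before the first infusion: 0.

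For a week-6 form, 2/6 to 3/6 of planned FOLFOX in the 6-treatment arms, and 2/12 to 3/12 in the 12-treatment arms, precedes the exposure measurement. The 14-16 month form is not the relevant one: 12 × 14 = 168 days, so FOLFOX given on schedule is over by then.

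**2. Which exposures are open to the problem.**

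- Diet: the food items ask about average intake over the past year (Appendix IV, Section 4.1). For a day-42 form, time on chemotherapy is 42 − 14 = 28 to 42 − 0 = 42 days, so 28/365 = 7.7% to 42/365 = 11.5% of the recall period.
- BMI: the schedule in Section 6.0 has height and weight measured before registration.
- Activity and supplements: Appendix IV gives no recall period.

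**3. Possible size, with no true effect.** The inputs are:

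- toxicity prevalence 0.30, borrowed from the grade 3+ assumption in Appendix II, Section 6.0;
- f, the share of toxicity cases that begin before the form (assumed);
- s, the fall in reported activity in those cases, in SD units (assumed);
- n = 1,500 (60% of 2,500, as in Appendix II) or 2,250 (90% of 2,500, from the completion rate that Appendix IV, Section 4.1, quotes for the preceding adjuvant trial).

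The odds ratio compares the top with the bottom activity quintile in 2,000,000 simulated patients. The false-positive rate uses a mean difference d = f × s and SE = √(1/(0.3n) + 1/(0.7n)), at two-sided 0.05. For example, with f = 0.25, s = 0.2 and n = 1,500: d = 0.05, SE = 0.0563, d/SE = 0.89, and the rate is Φ(0.89 − 1.96) + Φ(−0.89 − 1.96) ≈ 14%.

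| f | s | Null odds ratio | False positive, n = 1,500 | n = 2,250 |
|---|---|---|---|---|
| 0.10 | 0.05 | 0.98 | 5.1% | 5.1% |
| 0.25 | 0.1 | 0.93 | 7.3% | 8.4% |
| 0.25 | 0.2 | 0.87 | 14.4% | 19.2% |
| 0.50 | 0.2 | 0.75 | 42.7% | 58.5% |
| 0.50 | 0.5 | 0.50 | 99.3% | about 100% |

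For scale, s = 0.5 is a large shift: it would move the share of patients classed as inactive from 40% to about 60%, since 0.253 + 0.253 = 0.51 SD. Leaving out the early-onset cases returns the odds ratio to 0.996-1.002 in every scenario run. That follows from the set-up, in which only early cases have a distorted exposure; it confirms the mechanism and says nothing about its size in this trial.

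**The case against.** The strongest reply is that the analysis is labelled exploratory, sits in an optional companion study, and has no bearing on the trial's disease-free or overall survival results. That is right, and it limits how much weight the point can bear.

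Much of the exposure list is also protected. Diet has past-year recall, and Appendix IV, Section 4.1, reports that the instrument's nutrient measures performed in 200 patients on cytotoxic chemotherapy much as they do in healthy populations. BMI can come from pre-registration measurements. The activity items were validated against recalls and diaries spread over a year, which is compatible with a long reference period, although the documents do not state one. Cumulative neuropathy that first appears after the form keeps the right order, and a form completed at the first infusion follows no treatment at all. These points stand.

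A reader might infer from Section 9.1, where acute sensory neuropathy appears within hours to 2 days in about 56% of patients, that most patients have the outcome before the form. The text does not support this. That figure describes a reversible syndrome that usually clears within 14 days and carries no grade threshold, whereas Appendix V concerns cumulative neuropathy and the pharmacogenetic neuropathy endpoint in Appendix III is grade 2 or higher.

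None of this supplies the missing time order for activity and supplements.

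**Conclusion.** The point holds in a limited form. As written, Objective 1.4 and the incidence part of Appendix V, Objective 1.3, can count toxicity that began before the exposure was recorded, by up to 3 treatments. Reverse causation is a real and unaddressed possibility for physical activity and supplement use, limited for diet, and avoidable for BMI.

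Its size is not known. The range of 0.98 to 0.50 for the null odds ratio rests on assumed values of f and s that no document supplies. The lower end needs half of all cases to start before the form together with a half-SD shift in reported activity. A reader might conclude that the whole objective is uninterpretable, or that its associations would be false. The documents do not support that, given the past-year diet items, the pre-registration weight, and later-onset toxicity that follows the form.

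**What to change.** Add a short paragraph to Appendix IV, Section 4.4, with a cross-reference in Appendix V:

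- For activity and supplement exposures, define the outcome as toxicity at a stated grade threshold (for example grade 2+ neuropathy, or grade 3+ for other events) first reported after the questionnaire date. Exclude only patients who had already reached that grade.
- Report this beside the all-toxicity model or, at minimum, as a reverse-causation sensitivity analysis parallel to the one for plasma markers.
- Use pre-registration height and weight for BMI.
- State the recall period of the activity and supplement items.
- Leave the neuropathy-resolution analysis in Appendix V unrestricted.

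No change to Section 5.9 is proposed: Appendix VI gives an accrual period ending 6/2015, so new completion instructions would come too late.

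The cost is wording and precision. Adverse-event forms cover two cycles (Section 5.7), so onset may be datable only to a form period. With FOLFOX starting on day 0, the periods begin on days 0, 28 and 56 in the 6-treatment arms. A day-42 form then leaves one of three periods starting after it, against four of six in the 12-treatment arms. The plan should say how events in the period that straddles the form are handled. Excluding patients already at the threshold also leaves a somewhat less susceptible group, which is a reason to show both models. The sponsor must confirm that the questionnaire completion date is recorded, because the documents do not say so.

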APPENDIX V**CANCER PREVENTION COMPANION STUDIES (COLONOSCOPY): CALGB 71002**

Colon cancer survivors experience multiple risks beyond their initial surgical and chemotherapy treatments. Survivors can continue to have issues with neuropathy that may take years to resolve, if ever. Even in the absence of a familial syndrome, they have an increased risk of subsequent colorectal adenomatous polyps, new primary colorectal tumors and other primary tumors compared to the general population. CALGB/SWOG C80702 is collecting a risk set of data that can also be utilized to study these late effects in colon cancer survivors who have completed therapy. The database provides a unique opportunity to examine the impact of energy balance factors, medications and diet, which have previously been studied in a non-cancer population, in colon cancer survivors.

1.0 OBJECTIVES

- 1.1 Estimate the incidence density rate for each of second primary cancers and adenomatous polyps in colon cancer survivors.
- 1.2 Explore the impact of celecoxib, dietary factors, energy balance, physical activity, and vitamin D on second primary cancers and adenomatous polyps in colon cancer survivors.
- 1.3 Explore the role of celecoxib, physical activity, and vitamin supplementation on the incidence of peripheral neuropathy and time course of improvement/resolution.
- 1.4 Assess the influence of diet, body mass index, physical activity and other lifestyle habits on disease-free and overall survival among patients with stage III colon cancer (see [Appendix IV](#)).

2.0 BACKGROUND**2.1 Second primary cancers in colon cancer survivors**

The rate of second cancers after the diagnosis of colon cancer has been poorly defined. Older series have suggested colon cancer survivors have an increased risk of small bowel, bowel, cervical, uterine, ovarian and prostate cancers, compared to the general population.³¹¹⁻³¹⁴ While common risk factors may explain these observations, many of these studies were conducted prior to the recognition of genetic syndromes that link some, but not all, of these cancers to colon cancer. More defined collection of these data would facilitate understanding the true rates of second primary cancers in colon cancer survivors. Further, one needs to understand whether these cancers relate to an underlying genetic predisposition and/or modifiable diet/lifestyle/other exposure risk factors.

2.2 Polyps in colon cancer survivors

The rates of detection of adenomatous polyps after the diagnosis of colorectal cancer range from 20-30% within the first 3 years after diagnosis.^{315,316} Further, survivors of colorectal cancer have an increased lifetime risk of colorectal polyps and cancer above the general population.

2.3 Cumulative neuropathy from oxaliplatin

While oxaliplatin has had definitive influence on disease-free survival as adjuvant therapy for colon cancer, it adds toxicities that can persist well past the treatment period. At the completion of therapy in the MOSAIC trial, 12% of patients had grade 3 peripheral neuropathy and 92% had some level of neuropathy.³¹⁷ In a recent update, 15% of patients still had some level of residual neuropathy 4 years after the completion of adjuvant therapy.³¹⁸ Multiple agents have been tested to influence the development and/or severity of the cumulative neuropathy with limited efficacy.

3.0 METHODS

3.1 Utility of prevention-related studies embedded in a treatment trial

CALGB/SWOG C80702 provides an ideal opportunity to study factors influencing secondary cancers and long-term treatment-related toxicities of therapy. The primary interventions and the correlative science companion studies, including molecular markers (tumor and host-related) and dietary and lifestyle exposures, are testing these factors' influence on disease-free survival related to the index cancer. However, given the relatively high long-term cure rate of patients, rates of later adenomatous polyps, secondary cancers and oxaliplatin-related neurotoxicity are important considerations for colorectal cancer survivors. While there is a wealth of data on the influence of diet, lifestyle, aspirin/COX inhibitors, anthropometrics and other exposures on the risk of developing colorectal cancer (see protocol background and [Appendix IV](#)), most of those observational studies exclude patients with prior colorectal cancer. Thus, those data report only on the influence of these factors on an initial diagnosis of colorectal cancer. Whether such factors have a similar impact on subsequent polyps or malignancies (colorectal and non-colorectal) is not known. Potential research questions that arise in considering this issue include:

1. In a patient whose colon cancer has low COX-2 expression by IHC, does celecoxib lower the risk of subsequent polyps in those patients similar to those whose tumors had higher expression of COX-2?
2. Does physical activity reduce the rate of breast cancer in female colon cancer survivors by similar magnitude as in observational studies reporting breast cancer and physical activity in an initially non-cancer population?
3. What is the influence of vitamin D levels on the risk of polyps in colorectal cancer survivors?

Further, while one of the goals of CALGB/SWOG C80702 is to explore ways to minimize oxaliplatin-related toxicities (by testing reduction in number of cycles), it will be important to explore other exposures that may minimize oxaliplatin-related neuropathy. In [Appendix III](#) of the protocol (Vitamin D pathway) and [Appendix IV](#) of the protocol (Diet and Lifestyle), we propose to study whether AGXT 154 C/T or T/T polymorphisms ([Appendix IV](#)) and/or physical activity ([Appendix IV](#)) influences the incidence of grade 2+ peripheral neuropathy. Other hypotheses may also arise over the course of CALGB/SWOG C80702 that will be important to test, with the availability of tumor blocks, blood samples and diet/lifestyle questionnaires in this population.

3.2 Ascertainment of endpoints

For this companion study, we propose to collect data on (1) polyps and new primary colorectal cancer in colon cancer survivors, (2) secondary cancers in colon cancer survivors, (3) cumulative neuropathy after exposure to oxaliplatin and (4) disease-free and overall survival as defined in the treatment protocol.

For the first endpoints, we will request colonoscopy reports for all patients who consent to Question #1. Guidelines on the timing of colonoscopies vary across organizations. In 2005, ASCO recommended a repeat colonoscopy at 3 years and, if normal, every 5 years thereafter.³¹⁹ NCCN recommends a colonoscopy within 1 year of diagnosis and if normal, within 3 years and then every 5 years thereafter.³²⁰ The United States Multi-Society Task Force on Colorectal Cancer also recommended colonoscopy within 1 year of diagnosis, then 3 years later if normal and then every 5 years thereafter.³²¹ For all of these guidelines, the timing should be influenced by findings as well as other factors (including whether the patient has high-risk features like hereditary nonpolyposis colorectal cancer syndrome, inflammatory bowel disease and other conditions). Further, symptoms may dictate the use of colonoscopy earlier than the proposed

time frames. As such, in CALGB/SWOG C80702, we will strongly recommend adherence to the NCCN and US Multi-Society Task Force guidelines (which should result in at least 2 colonoscopies within the first 4 years after diagnosis).

For the second endpoint (other cancers besides colorectal cancer), the follow-up form will inquire about other cancers. For patients who enroll on this substudy and develop other cancers in the 6-year follow-up period, we will request pathology records and documentation to confirm self-reports of cancer as well as staging.

For the third endpoint (cumulative neuropathy), toxicity forms during therapy and follow-up and recurrence data forms will be collected. Neuropathy will be graded based on the CTCAE Version 4.0:

Grade 1: asymptomatic; loss of deep tendon reflexes or paresthesia.

Grade 2: moderate symptoms; limiting instrumental activities of daily living.

Grade 3: severe symptoms; limiting self-care activities of daily living.

Grade 4: life-threatening consequences; urgent intervention indicated

Disease-free and overall survival are defined in [Section 13.0](#) of the protocol. [Appendix IV](#) addresses the methods for diet, lifestyle and medication use as related to disease-free and overall survival.

